1.3 Number of Subjects

In total 206 PFS events in the study would have 90% power to show statistically significant PFS at the 2-sided 5% level if the assumed true treatment effect were hazard ratio (HR) 0.62; this translates to a 8 month benefit in median PFS over 13 months on placebo (estimated from data reported by Alsop et al 2012) if PFS is exponentially distributed.

Approximately 344 patients will be recruited (2:1 ratio) so that data maturity for the PFS analysis is approximately 60%. When global enrolment closed on 14 November 2014, patients still in screening were permitted to be randomised and therefore a total of 391 patients were randomised as part of Global recruitment.

Assuming 18 months non-linear recruitment, 206 PFS events are expected to occur approximately 36 months after first subject in is enrolled in the study (FSI). At this time, an interim analysis of OS will also be performed.

PFS will be analysed when approximately 196 events have occurred or after the last patient randomised has had the opportunity to have been on the study for at least 36 months, whichever comes first. No further analyses of PFS are planned beyond this point unless requested by Health Authorities.

A further interim analysis of OS may be performed at approximately 206 events (~53% maturity of the 391 patients randomised). Assuming that the true OS treatment effect is 0.85 and this point estimate for the HR of 0.85 was observed, the 95% UCL for the HR would be 1.13. A final OS analysis may be performed at approximately 60% maturity (~235 events/391 patients who were randomised in SOLO1). Assuming that the true OS treatment effect is 0.85 and this point estimate for the HR of 0.85 was observed, the 95% UCL for the HR would be 1.11. Note that these estimates are based on the assumption that no confounding will occur. AstraZeneca considers there will be potential confounding of OS data due to availability of PARP inhibitors for BRCA mutated ovarian cancer patients during follow up in this study, which are likely to disproportionately affect OS in one arm of the study (placebo-treated patients).

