4 ANALYSIS METHODS

Statistical Analysis Plan

PFS will be analysed when approximately 196 events have occurred or after the last patient randomised has had the opportunity to have been on the study for at least 36 months, whichever comes first. No further analyses of PFS are planned beyond this point unless requested by Health Authorities.

An initial analysis of OS, PFS2, TFST and TSST will be performed at the same time as the primary analysis of PFS and will use the same methodology and model.

Supportive analyses of time to earliest progression by RECIST or CA-125 or death and TDT will be provided, using the same methodology as specified for the primary analyses of PFS; however no multiple adjustment will be applied as these are viewed as supportive endpoints.

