For each subgroup, the HRs (olaparib: placebo) and associated CIs will be calculated from a Cox Proportional Hazards model (ties = Efron) that contains the treatment term, factor (subgroup) and treatment-by-factor interaction term. The treatment effect HRs for each treatment comparison along with their CIs will be obtained for each level of the subgroup from this single model. The HRs and 95% CIs will be presented on a forest plot including the HR and 95% CI from the overall population (using the primary analysis). In addition, summaries of the number and percentage of patients experiencing a PFS event for each subgroup will be provided along with the median PFS for each treatment.

No adjustment to the significance level for testing will be made since all these subgroup analyses will be considered exploratory and may only be supportive of the primary analysis of PFS.

The presence of quantitative interactions will be assessed by means of an overall global interaction test. This will be performed in the overall population by comparing the fit of a Cox Proportional Hazards model including treatment, all covariates, and all covariate-by-treatment interaction terms, with one that excludes the interaction terms and will be assessed at the 2-sided 10% significance level. If a covariate does not have ≥20 events per level (of the covariate) it will be included as a covariate in the model but the covariate-by-treatment interaction term will be omitted. If the fit of the model is not significantly improved then it will be concluded that overall the treatment effect is consistent across the subgroups.

If the global interaction test is found to be statistically significant, an attempt to determine the cause and type of interaction will be made. Stepwise backwards selection will be performed on the saturated model, whereby (using a 10% level throughout) the least significant interaction terms are removed one-by-one and any newly significant interactions re-included until a final model is reached where all included interactions are significant and all excluded interactions are non-significant. Throughout this process all main effects will be included in the model regardless of whether the corresponding interaction term is still present. This approach will identify the factors that independently alter the treatment effect and prevent identification of multiple correlated interactions.

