4.2.4 Overall survival (OS)

OS data will be analysed at the time of the primary analysis of PFS and will use the same methodology and model (provided there are sufficient events available for a meaningful analysis [≥20 deaths], if not descriptive summaries will be provided). A further interim analysis of OS will be performed when ~206 events are observed (approximately 53% maturity of the 391 patients randomised) and a final analysis of OS will be performed when the OS data are approximately 60% mature (~235/391 patients randomised).

An additional descriptive analysis for OS will also be performed at 7 years post the last patient randomised as part of global enrolment (DCO March 2022).

As a key sensitivity, the analysis of OS will be repeated in those patients whose gBRCAm status is confirmed by Myriad centrally. A KM plot of OS in this subset of patients will be presented by treatment group. This sensitivity analysis will also be repeated excluding any patients who did not have a tBRCA mutation status confirmed by Foundation Medicine.

The remaining sensitivity analyses outlined for PFS in Section 4.2.2 will not be repeated for OS with the exception of a KM plot of the time to censoring where the censoring indicator of the primary OS is reversed (what was originally a censored event in the primary PFS2 analysis becomes an actual event and what originally was a PFS2 event becomes a censored event).

A summary of survival status at the time of analysis will be produced. This will summarise the number of patients who have died, who are still in survival follow-up, who are lost to follow-up or who have withdrawn consent.

In addition, duration of follow-up will be summarised using medians:

- In censored (not died) patients only: Time from randomisation to date of censoring (date last known to be alive)
- In all patients: Time from randomisation to the date of death or to the date of censoring for censored patients.

At the time of the last analysis of OS, the subgroup analyses and global interaction test detailed for PFS in Section 4.2.2 will be repeated for OS.

Exploratory analyses of OS

Exploratory analyses of OS adjusting for impact of subsequent PARP inhibitor trial or treatment may be performed if a sufficient proportion of patients switch. The decision to adjust and final choice of methods will be based on a blinded review of the data and the plausibility of the underlying assumptions. Baseline and time-dependent characteristics will

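### A non-significant global interaction test is read as proof of a consistent effect, but at the design HR of 0.62 the test would usually miss a subgroup with no benefit

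*SAP*

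**What the plan says.** SAP 4.2.2 gives the purpose of the subgroup analyses as assessing whether the effect is consistent across prognostic factors, and it lists 11 factors. Each factor gets a Cox model with a treatment-by-factor interaction, and the level-specific HRs and 95% CIs go on a forest plot.

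A global test then sets the Cox model holding all interactions against "one that excludes the interaction terms and will be assessed at the 2-sided 10% significance level". The plan also fixes how a non-significant result is to be read: when the "fit of the model is not significantly improved then it will be concluded that overall the treatment effect is consistent across the subgroups". A search for the responsible factor follows only when the test is significant. Where a covariate has fewer than 20 events in a level, the SAP keeps its main effect but omits its interaction.

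Protocol 12.2.2 has the same conclusion rule. SAP 4.2.4 adds that, at the last OS analysis, "the subgroup analyses and global interaction test detailed for PFS in Section 4.2.2 will be repeated for OS".

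The only power statement concerns the overall effect. SAP 1.3 says "In total 206 PFS events in the study would have 90% power to show statistically significant PFS at the 2-sided 5% level". That statement is tied to one design value, namely "if the assumed true treatment effect were hazard ratio (HR) 0.62". SAP 4 says "PFS will be analysed when approximately 196 events have occurred", or once the last patient randomised could have had 36 months on study, if that comes first. No power or detectable interaction is stated for the global test.

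**The concern.** Failing to reject a null hypothesis of no interaction is not evidence that there is none, unless the test had a good chance of finding an interaction that matters. The rule has no margin and no confidence limit, and no power is stated to stand in for them. Yet it is the only written rule in either document that yields a conclusion of consistency.

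Two features weaken the test further. One real interaction is tested jointly with all the others, so its signal is spread over many degrees of freedom. The conclusion also refers to the subgroups generally, although the interactions of sparse factors are left out of the test.

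The stake is a report stating that the effect is consistent when a sizeable group of patients gains nothing. The OS repeat matters most, because it still lies ahead.

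**Working it through.** **Inputs from the documents.** Test level 10%; 2:1 allocation; about 196 PFS events; design HR 0.62 with 206 events for 90% power; about 235 events at the final OS analysis.

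**Assumptions.** The documents give no subgroup sizes, so the affected subgroup is taken to hold a share f of 10% to 50% of events. Its HR is 1.0. Interaction degrees of freedom are not stated. If gBRCA status and race drop out for sparse levels, 9 of the 11 factors remain, giving about 9 df when each has two levels. A range of 1 to 15 df is shown.

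**Step 1: reproduce the design figure.** Events = (1.960 + 1.282)² / [(2/3)(1/3)(ln 0.62)²] = 10.51 / (0.2222 × 0.2285) = 207, against 206 stated. Power is 89.9% at 206 events and 88.4% at 196.

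**Step 2: signal in the interaction test.** With D events in all, the log HR in a level holding share f has variance 4.5/(D f). The difference between two levels has variance 4.5/[D f(1 − f)]. The noncentrality is therefore

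λ = D × (2/9) × f(1 − f) × [ln(HR_sub/HR_rest)]².

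The miss rate is the probability that a noncentral chi-square with k df and noncentrality λ falls below the 10% critical value.

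Example with f = 0.30, HR 1.0 versus 0.62: λ = 196 × 0.2222 × 0.21 × 0.2285 = 2.09. On 9 df the critical value is 14.68 and the miss rate is 78.3%.

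**Step 3: PFS, 196 events, HR 1.0 versus 0.62 elsewhere.**

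| Share of events | λ | 1 df | 5 df | 9 df | 15 df |
|---|---|---|---|---|---|
| 10% | 0.90 | 75.3% | 83.5% | 85.3% | 86.5% |
| 20% | 1.59 | 64.7% | 78.1% | 81.3% | 83.5% |
| 30% | 2.09 | 57.8% | 74.1% | 78.3% | 81.2% |
| 50% | 2.49 | 52.6% | 70.9% | 75.9% | 79.4% |

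With no interaction at all, the nominal non-significance rate is 90%, so the result hardly separates the two situations. Simulated Cox models (391 patients, 196 events, 1,000 trials per scenario) gave miss rates of 78.5%, 73.5% and 70.1% for 20%, 30% and 50% subgroups with 8 binary factors. With 10 factors they were 79.9%, 73.0% and 75.2%. For a 30% subgroup, 80% power would need about 580 events on 1 df or about 1,206 on 9 df.

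**Step 4: how far this depends on the effect elsewhere (196 events, 9 df).**

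- HR 0.31 elsewhere, the value protocol 1.3.1 takes from the upper confidence limit of the phase II result: 57.3%, 33.5%, 21.1% and 14.0% missed for shares of 10%, 20%, 30% and 50%.
- Whole-trial HR held at 0.62, so that HR_rest = 0.62^(1/(1 − f)): 76%, 65%, 50% and 32% missed for shares of 20%, 30%, 40% and 50%.
- The miss rate drops below 50% once the HR elsewhere is below about 0.28, 0.38, 0.43 or 0.46 for shares of 10%, 20%, 30% or 50%.

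**Step 5: OS, 235 events, 9 df, HR 1.0 versus an assumed 0.70 elsewhere.** λ = 0.60, 1.06, 1.40 and 1.66; miss rates are 86.9%, 84.4%, 82.5% and 80.9% for shares of 10%, 20%, 30% and 50%. The 0.70 is not a document figure. The SAP's illustrative OS HR is 0.85 for the whole trial; for a 30% no-benefit subgroup that implies 0.85^(1/0.7) = 0.79 elsewhere, a smaller contrast that is harder to detect.

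**The case against.** The strongest reply is that little hangs on this sentence. The SAP labels the subgroup analyses exploratory, the testing hierarchy does not use them, and the 10% level is already relaxed. The forest plot shows each analysed level's HR and 95% CI whatever the test says, so a reader could see an HR near 1. Holding back the factor search until the global test is significant is a defensible guard against false positives. All of this stands and limits the weight of the point. None of it changes a rule that prescribes a conclusion, and the figures above already use the 10% level.

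A second reply is that the miss rates rest on assumed subgroup sizes, df and effects. This also stands. A reader might infer that the test misses a no-benefit subgroup more than half the time in general. The documents do not support that: with HR 0.31 elsewhere, or a whole-trial HR of 0.62 and a subgroup above about 40% of events, the miss rate is below 50%. On the other hand, 0.31 comes from a phase II study in relapsed disease, and this trial was sized on 0.62. At 0.62 the rate stays above 50% for every share and df in the table.

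A third reply is timing. SAP section 5 speaks of the PFS analysis as past, so the PFS rule can no longer be changed prospectively. That is right. What remains open is how the PFS result is worded and the OS repeat.

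**Conclusion.** The point holds in conditional form. The plan turns a non-significant 10% global test into a conclusion of consistency, states no power for that test, and at the design effect the test cannot support the conclusion. With 196 events, about 9 df and HR 1.0 versus 0.62, a no-benefit subgroup is missed about 76% to 85% of the time for shares of 50% down to 10%. For OS under the stated assumptions it is about 81% to 87%. If the effect elsewhere is as strong as 0.31, the PFS figures are 14% to 33.5% for shares of 50% down to 20%.

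The calculation assumes two-level, independent factors and a Schoenfeld-type variance. Overlapping factors, such as the two region splits, would tend to lower power further.

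A reader might also infer that the effect is in fact inconsistent, or that a formal efficacy claim is at risk. Neither follows. The documents hold no subgroup results, and PFS, PFS2 and OS are tested without reference to this rule.

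**What to change.** In SAP 4.2.2 and protocol 12.2.2, and so for the OS repeat in SAP 4.2.4, replace the conclusion sentence with:

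> A non-significant global test will be reported as no statistical evidence of heterogeneity and will not be taken to show consistency.

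For every analysed factor, report the ratio of HRs between levels with its 95% CI, from the interaction models already specified and whatever the global test shows. This shows the reader what the data can exclude. For a 30/70 split at 196 events the standard error is √(4.5/(196 × 0.21)) = 0.331, so an observed ratio of 1 would have a CI of about 0.52 to 1.91. That interval still contains 1/0.62 = 1.61. Apply both changes to the pending OS analysis and to the reporting of PFS.

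Do not add a rule that each level's upper 95% limit must be below 1. With a truly uniform HR of 0.62, a level holding 20%, 30% or 50% of events would pass only 29%, 41% or 61% of the time, so small levels would fail through size alone.

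The cost is a wording change and one extra column from planned models. The downside is a more cautious statement and several exploratory CIs without multiplicity control, which fits their stated status.

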12.2.2.1 Sensitivity Analyses for Primary Endpoint

As a sensitivity analysis to the primary endpoint of PFS, the primary analysis will be repeated excluding any patients who did not have a gBRCA mutation status confirmed by the central Myriad test. The same methodology and model will be used and the HR and associated 95% CI from a Cox Proportional Hazards model will be reported. A KM plot of PFS in this subset of patients will be presented by treatment group.

Sensitivity analyses will be performed to assess the possible presence of time-assessment bias (i.e., differential assessment times between treatment groups).

Summary statistics for the number of weeks between the time of progression and the last evaluable RECIST assessment prior to progression will be presented for each treatment group.

- (a) Evaluation-Time bias

Sensitivity analyses will be performed to assess possible evaluation-time bias that may be introduced if scans are not performed at the protocol-scheduled time points. The midpoint between the time of progression and the previous evaluable RECIST assessment will be analysed using a stratified log rank test, as described for the primary analysis of PFS. This approach has been shown to be robust to even highly asymmetric assessment schedules (Sun and Chen 2010). This approach will use the investigator RECIST assessments.

(b) Attrition bias

Attrition bias will be assessed by repeating the primary PFS analysis except that the actual PFS event times, rather than the censored times, of patients who progressed or died in the absence of progression immediately following two, or more, non-evaluable tumour assessments will be included. In addition, patients who take subsequent therapy prior to progression or death will be censored at their last evaluable assessment prior to taking the subsequent therapy.

Additionally a Kaplan-Meier plot of the time to censoring where the censoring indicator of the primary PFS analysis is reversed will be presented.

(c) Ascertainment bias

A stratified log-rank test will be repeated using BICR assessed RECIST data to programmatically derive PFS. The HR and 95% Confidence Interval will be presented.

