Attrition bias will be assessed by repeating the primary PFS analysis except that the actual PFS event times, rather than the censored times, of subjects who progressed or died in the absence of progression immediately following two, or more, non-evaluable tumour assessments will be included. In addition, subjects who take subsequent therapy prior to their last evaluable RECIST assessments or progression or death will be censored at their last evaluable assessment prior to taking the subsequent therapy. Additionally a KM plot of the time to censoring where the censoring indicator of the primary PFS analysis is reversed (what was originally a censored event in the primary PFS analysis becomes an actual event and what originally was a PFS event becomes a censored event) will be presented.

(c) Ascertainment bias

A stratified log-rank test will be repeated using BICR RECIST data to programmatically derive PFS. The HR and 95% CI will be presented.

The type of event (RECIST or death) will also be provided.

If there is an important discrepancy between the primary analysis using investigator assessments and this sensitivity analysis using BICR assessments, then the proportion of subjects with site but no central confirmation of progression will be summarised. This scenario is possible as at the time of the primary analysis data cut off all scans will be sent for central review assessment regardless of whether or not a patient has been assessed as having progressed by the site. The approach of imputing an event at the next visit in the BICR assessed analysis may help inform the most likely HR value, but only if an important discrepancy exists.

Disagreements between investigator and BICR assessment of RECIST progression will be presented for each treatment group. The summary will include the early discrepancy rate which is the frequency of BICR progressions declared before the investigator review progressions (≥2 weeks earlier and including progressions declared by BICR but not investigator) as a proportion of all BICR progressions, and the late discrepancy rate which is the frequency of BICR progressions declared after the investigator review (≥2 weeks later and including progressions declared by investigator but not BICR as a proportion of all discrepancies (including early and late discrepancies) (Amit et al 2011).

(d) Deviation bias (if meaningful to do)

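### The attrition-bias analysis of PFS changes two censoring rules in one run, so its single hazard ratio cannot isolate attrition bias and may mask or exaggerate it

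*SAP*

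**What the plan says.** The primary PFS definition (SAP 3.2.1; protocol 11.1.1) sets two rules that matter here. An event after two or more missed visits is not counted, and the patient is censored at the latest evaluable assessment. An event after another anticancer therapy is counted.

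The attrition-bias analysis reverses both rules at once. SAP 4.2.2(b) repeats the primary analysis with actual event times put back for patients whose progression or death followed two or more non-evaluable assessments. It then adds that "subjects who take subsequent therapy prior to their last evaluable RECIST assessments or progression or death will be censored at their last evaluable assessment" before the therapy began. Protocol 12.2.2.1(b) has the same two-part rule: "patients who take subsequent therapy prior to progression or death will be censored at their last evaluable assessment" before that therapy.

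SAP Table 7 and protocol Table 12 each list this as one analysis. Neither document plans an HR in which only the missed-visit rule is changed.

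The SAP does plan related descriptive output by arm:
- a Kaplan-Meier plot of time to censoring, with the censoring indicator reversed (4.2.2(b));
- counts of patients missing one, and two or more, assessments (4.2.2, PFS sensitivity analyses);
- reasons for censoring and numbers prematurely censored (4.2.2);
- counts of patients starting further therapy before or after progression (4.2.5).

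**The concern.** The two changes answer different questions. Restoring events asks whether the missed-visit rule distorts the primary estimate, which is the attrition question. Censoring at subsequent therapy replaces the primary treatment-policy handling with another estimand. Protocol 6.3.2 requires patients who start another therapy to be followed to RECIST progression, so this second change discards events that were observed.

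That censoring is plausibly informative. CA-125 is sampled at the start of each 28-day period on treatment (protocol 6.4.6.4), while scans are 12-weekly. Once study treatment has stopped, further therapy is at the investigator's discretion (protocol 3.1, 5.5.2.1). Therapy can then begin on a marker or symptom signal shortly before RECIST progression, and censoring at that point removes a patient who is about to have an event.

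With both changes in one run, an unchanged HR does not rule out attrition bias, and a changed HR cannot be assigned to either rule. The primary result could be called robust, or fragile, for the wrong reason.

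**Working it through.** **1. The design figure.** SAP 1.3 states: "In total 206 PFS events in the study would have 90% power to show statistically significant PFS at the 2-sided 5% level". The design effect given there is a hazard ratio of 0.62, from medians of 13 months on placebo and 13 + 8 = 21 months on olaparib. With 2:1 allocation the Schoenfeld formula is

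events = (1.960 + 1.282)² / [(2/3)(1/3)(ln HR)²].

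- HR 0.62: 10.51 / (0.2222 × 0.2285) = 206.9, so 207.
- HR 13/21 = 0.619: 206.
- Power with 206 events at HR 0.62: 89.9%.

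The stated 206 is reproduced. It fixes the design medians used below but does not itself bear on the point.

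**2. Simulation set-up.**
- *From the documents:* medians of 13 and 21 months with exponential PFS, 2:1 allocation, 18 months' recruitment, analysis 36 months after the first patient, 12-weekly scans.
- *Assumed:* uniform accrual (the plan says non-linear), an unstratified Cox model, progression detected late after missed scans, and therapy starting just before progression.
- *Also assumed:* the rates of missed scans and early therapy, because neither document gives any.

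Samples were very large, so the table shows systematic shifts and not sampling noise.

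**3. Results.** Rates are olaparib / placebo, in per cent.

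| Case | Missed scans | Early therapy | Primary HR | Restore only | Censor at therapy only | Both |
|---|---|---|---|---|---|---|
| 1 | 10 / 2 | 8 / 2 | 0.590 | 0.622 | 0.557 | 0.591 |
| 2 | 2 / 10 | 2 / 8 | 0.684 | 0.653 | 0.722 | 0.684 |
| 3 | 2 / 10 | 2 / 10 | 0.684 | 0.653 | 0.736 | 0.697 |
| 4 | 10 / 2 | 2 / 10 | 0.590 | 0.622 | 0.634 | 0.668 |
| 5 | 12 / 2 | 2 / 2 | 0.579 | 0.619 | 0.578 | 0.620 |
| 6 | 5 / 5 | 5 / 5 | 0.637 | 0.639 | 0.636 | 0.638 |

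**4. Reading the table on the log scale.**
- *Masking (case 1).* Restoring shifts by ln(0.622/0.590) = +0.053 and therapy censoring by ln(0.557/0.590) = −0.058. The combined shift is ln(0.591/0.590) = +0.002. Case 2 is the mirror image.
- *Reversal (case 3).* Restoring alone shifts by ln(0.653/0.684) = −0.046, but the combined run shifts by ln(0.697/0.684) = +0.019.
- *Exaggeration (case 4).* The combined shift is ln(0.668/0.590) = +0.124, of which attrition is 0.053, or 43%.
- *No harm (cases 5 and 6).* With early therapy rare and balanced, the combined run gives 0.620 against 0.619 for restoring alone. With both rates balanced, nothing moves materially.

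Masking or reversal arises when both excesses are in the same arm, and exaggeration when they are in opposite arms.

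**5. Scale.** At about 196 events, SE(log HR) ≈ 1/√(196 × 2/9) = 0.15. The case 1 attrition shift is 0.053/0.15 ≈ 0.35 SE, and the largest combined shift shown (case 4) is 0.124/0.15 ≈ 0.8 SE. The highest combined HR, 0.697, would have an upper 95% limit near 0.697 × exp(1.96 × 0.1515) = 0.94. All estimates come from the same patients, so the SE does not measure chance differences between rows. It does show that these shifts are small against the precision of the primary result.

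**The case against.** The strongest reply has five parts.

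*The combined rule is deliberate and disclosed.* Both documents pre-specify it, and the Table 7 label refers to censoring rules in the plural. This stands: the run is not an error, and varying one rule at a time is a question of interpretability.

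*The run can still show attrition bias.* A reader might infer that combining the changes makes the analysis incapable of showing it. The documents do not support that: nothing in them says that early therapy is common or unbalanced, and where it is rare and balanced nearly the whole effect appears (case 5).

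*Other output covers the gap.* The by-arm summaries and the reverse-censoring plot would show whether either imbalance exists and in which arm. This stands in part. They can warn that masking is possible, but none gives an HR with only the missed-visit rule changed.

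*Early therapy is limited by the protocol.* Patients are to stay on treatment to RECIST progression despite CA-125 rises (3.1, 5.5.2.1), and other anticancer therapy is barred during study treatment (5.6.1, 5.6.6). This limits the rate without making it zero: protocol 6.3.2 provides for therapy before progression, and SAP 4.2.5 tabulates it.

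*It is late.* The SAP is dated 15 February 2022, and its Section 5 describes events after the PFS analysis. No further PFS analysis is planned unless health authorities ask (SAP 1.3). This stands, so a split would now be supplementary.

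**Conclusion.** The point holds in a limited form. The run labelled attrition bias mixes an attrition question with a change in how subsequent therapy is handled. Its single HR cannot isolate attrition bias, and it may mask, reverse or exaggerate it when missed scans or early therapy differ between arms.

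The illustrated component shifts run from about 0.03 to 0.05 on the HR scale in the unbalanced cases, and the largest combined shift is 0.078 (0.590 to 0.668). With both rates balanced, the effect is negligible. These sizes rest on assumed rates and on therapy starting just before progression. That the two changes can pull in opposite directions does not depend on the exact rates.

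A reader might go further and conclude that the robustness of the primary PFS result is in doubt. Nothing here supports that: the primary analysis is untouched, and the shifts are small against its standard error. This is a cheap improvement in interpretability.

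**What to change.** Report three labelled rows in place of one:
- **(b1)** the primary analysis with actual event times restored after two or more missed assessments, and no other change;
- **(b2)** the primary analysis with censoring at the last evaluable assessment before subsequent therapy, and no other change;
- **(b3)** the pre-specified combined run, as now written.

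Read (b1) as the attrition result, beside the by-arm counts of missed scans. Read (b2) beside the counts of therapy before progression, and state that its censoring may be informative.

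The cost is one or two extra table rows from data already held. The primary analysis and the alpha allocation do not change. Because the primary PFS analysis predates this SAP, (b1) and (b2) should be marked supplementary, and used in any further PFS analysis that health authorities request.
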